7.1 Subject Compliance Monitoring

μ Cor wear time will be assessed throughout the study period. Wear time will be monitored by the sponsor based on the daily data transmissions from the μ Cor device. It is anticipated that the wear time with μ Cor system will be over 70% through the study period. For subjects who show early signs of non-compliance, the sponsor will inform the site, who will then make phone-calls to encourage subjects to continue wear the μ Cor system. In addition, site with the support of sponsor's technical support will try to trouble shoot and alleviate the reasons for subject's non-compliance.

7.2 Managing μ Cor Therapy

NA

7.3 Dispensing, Storage and Return

7.3.1 Dispensing of Study Device

The investigator will be responsible for dispensing the study device.

7.3.2 Storage

Devices will be stored in an appropriate limited access room. Storage conditions will adhere to the guidelines outlined in the Clinical Manual.

7.3.3 Return of Study Device

Return of the device will occur during the final scheduled visit.

7.4 Device Malfunction or Defect

In case of device malfunction or defect, subjects will call the site for initial troubleshooting. If the site cannot resolve the issue, the sponsor will be contacted for further troubleshooting. In case the defect or malfunction cannot be resolved, the sponsor will provide new equipment. All device defects or malfunctions related to device defect or malfunction will be reported to the sponsor on the appropriate CRF.

8 Statistical Plan

8.1 Sample Size and Power Calculation

The sample size was chosen to answer the primary and secondary objectives. We expect a 50/50 distribution between patients enrolled with an LVEF less than 35% and an LVEF greater than 35%. After the 200th patient is enrolled, we will conduct an interim analysis to confirm the LVEF distribution.

The first 200 patients will generate a convenience sample of heart failure related clinical events. Assuming a 20% event rate within the first 30 days in patients with reduced LVEF, we estimate that we will observe at least 25-30 heart failure related events among patients with reduced EF through the length of the 90 day study period (accounting for not all patients reaching completion).

We believe that 25-30 heart failure related events will be enough events to draw meaningful correlations among μ Cor device measurements and heart failure related episodes.

Following the interim analysis, the additional 300 subjects will further generate heart failure related clinical events to answer the primary objective and be monitored for VT/VF arrhythmic events to answer the secondary objectives.

8.2 Randomization Scheme

The first 200 subjects in the US will exclusively wear the patch in the side position. In the following 300 subjects, the position of the patch location will be alternated by subject to either front or side location in a 1:1 scheme, stratified by site. Outside the US, all subjects will follow an alternating pattern of patch location wear.

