3.1 General Design

3.1.1 Study Description

Subjects meeting the inclusion/exclusion criteria will wear μ Cor for up to 90 days from the day of fitting. 500 total patients will be enrolled. There will be an interim analysis when the 200th subject has finished the study to assess for distribution of patients with reduced and preserved LVEF. The first 200 subjects enrolled in the US will exclusively wear the device in the side position. The subsequent subjects in the US will follow an alternating pattern of front position and side position placement.

Subjects will be fitted with μ Cor during discharge of a heart failure related hospitalization or within a clinic visit that has occurred within 10 days of a heart failure related hospitalization. The μ Cor fitting will mark day 0 of the study. An LVEF measurement will be recorded during enrollment or within 30 days post enrollment if an LVEF measurement has not been recorded within 30 days prior to enrollment. An investigator assessment will be performed during all clinic visits. The assessment template is shown in Appendix A.

Subjects will be given a diary at enrollment that will ask them to rate their degree of specific symptoms of heart failure such as shortness of breath and fatigue as well as mark any heart failure related clinical events or medication changes that have occurred since the last entry. The subject diary is shown in Appendix A.

Study follow up visits will occur at day 30, day 60, and day 90. There will be no follow up visit if the subject has stopped wearing the device. During follow up visits the subjects will be asked about any heart failure related clinical events or change in symptoms that have occurred since the last follow up. The subject will receive a study based weekly phone call asking the subject about any recent heart failure related clinical events or change in heart failure symptoms. During the weekly phone call the subject will be reminded to fill out the daily diary. No phone calls will be given on the week where there is a study follow up visit. There will be no follow up visit if the subject has stopped wearing the device. In case of adverse skin reaction to the μ Cor adhesive and/or electrodes, on the discretion of physician, subjects may discontinue wearing the device for

up to 48 hours. In the event the subject has stopped wearing the device completely, follow up phone calls will continue to be conducted per protocol in order to capture clinical information.

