6.2 Scheduled Visits and Phone Calls

The scheduled visits are summarized in Table I and include the initial visit along with visits at day 30, 60, and 90. There will also be weekly phone calls to the patient. No monthly visits or weekly phone calls will occur if the subject has stopped wear. The phone calls will be conducted within no more than 2 days before or after the scheduled date. The scheduled visits will be conducted within no more than 5 days before or after the scheduled date. During the optional extended 90 day wear period, scheduled clinic visits and weekly phone calls will continue to take place following the procedures in Visits 2-4 with the exception of 6.2.4.6 (asking again for additional wear). Chart review and a follow up phone call will take place at 6 months and 1 year post enrollment.

6.2.1 Visit 1: Screening, enrollment and start (To occur during hospital discharge for decompensated heart failure or during a clinic visit in an out-patient setting no more than 10 days post hospital discharge).

6.2.1.1 All subjects will complete the Kansas City HF and study specific questionnaire.

6.2.1.2 A chart review will be used to evaluate patients for enrollment. A screening log will be maintained.

- 6.2.1.3 Patients meeting the initial Inclusion/Exclusion criteria will be approached for consenting.
- 6.2.1.4 The initial clinical and demographic data will be recorded in every subject. These may be done by chart review and will include:
- 6.2.1.5 Demographic characteristics, including gender, age, height and weight will be recorded.
- 6.2.1.6 Medical history will be recorded, including comorbidities, heart disease and physical disability.
- 6.2.1.7 Medical therapy for heart failure will be recorded for all subjects.
- 6.2.1.8 LVEF measurement within the past 30 days will be recorded if available. If a previous LVEF is not available, one will be obtained within 30 days of enrollment.
- 6.2.1.9 Subjects will be given a physical assessment.
- 6.2.1.10 Subjects will be assigned to wear the patch at either the front or side location (alternating 1:1)
- 6.2.1.11 Subjects will be fitted with μ Cor at hospital discharge or departure from clinic.
- 6.2.1.12 Device fitting will follow current Instructions for Use (IFU) procedures.
- 6.2.1.13 The date and time when μ Cor wear began will be recorded.
- 6.2.1.14 A clinic visit appointment will be scheduled to coincide with the end of the first 30 days of μ Cor wear.

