8.3 Endpoint Assessment

8.3.1 Primary endpoint

The first primary endpoint will be assessed by the strength of the correlation between μ Cor device readings and heart failure related clinical events.

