8.4 Statistical Methods

For primary, secondary, and safety endpoints, descriptive statistics and qualitative analysis will be performed as appropriate.

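### Visit 1 step 6.2.1.10 alternates patch position 1:1 for every subject, contradicting the side-only rule for the first 200 US subjects in Sections 3.1.1 and 8.2 (about 250/250 against 350/150)

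*Combined protocol and SAP*

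**What the plan says.** Three places in the combined protocol and SAP set the patch position.

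- Section 3.1.1: "The first 200 subjects enrolled in the US will exclusively wear the device in the side position". Later US subjects alternate between front and side.
- Section 8.2 repeats the side-only rule for the first 200 US subjects and then states: "In the following 300 subjects, the position of the patch location will be alternated by subject to either front or side location", 1:1 and stratified by site. It adds: "Outside the US, all subjects will follow an alternating pattern of patch location wear".
- Section 6.2, Visit 1, step 6.2.1.10: "Subjects will be assigned to wear the patch at either the front or side location (alternating 1:1"). It makes no exception for the US lead-in and does not refer to 8.2.

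On analysis, Section 8.3.1 says: "The first primary endpoint will be assessed by the strength of the correlation between" device readings and heart failure events. Section 8.4 says that "descriptive statistics and qualitative analysis will be performed as appropriate", and Section 8.5 (additional analysis) is marked not applicable. Position does not appear in any of these sections. Readings are repeated within a subject, as Section 7.1 shows: "Wear time will be monitored by the sponsor based on the daily data transmissions from the" device, with wear time that it anticipates "will be over 70% through the study period". No unit of analysis, test or interval is named.

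**The concern.** Step 6.2.1.10 is the instruction that site staff follow when they fit the device. A US site working from it alone would start alternating at its first subject. The all-side US block of 3.1.1 and 8.2 would then not exist, and the number of front-position subjects would change.

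There is a smaller point about the analysis. Under 3.1.1 and 8.2 every front-position subject is either a non-US subject or a later US enrollee, so position is partly mixed with region and calendar time. Sections 1.2 and 1.3 describe validation on the left lateral torso of sheep and on the left chest of patients, and give no front-versus-side comparison. The trial goes to the trouble of allocating position, yet does not say that results will be shown by position.

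**Working it through.** **Inputs.** Total 500 subjects (Section 5.2). US lead-in of 200, side only (3.1.1, 8.2). All others alternate 1:1 (8.2). The number of US subjects, U, is not given; the Study Summary says only 30 to 50 centers, multinational.

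**The plan's own total.** 200 + 300 = 500, which agrees with Section 5.2.

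**Allocation under 3.1.1 and 8.2.** With L = min(U, 200), side = L + (500 − L)/2 and front = (500 − L)/2.

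| US subjects | Side | Front |
|---|---|---|
| 200 or more | 200 + 150 = 350 | 150 |
| 150 | 150 + 175 = 325 | 175 |
| 100 | 100 + 200 = 300 | 200 |
| 50 | 50 + 225 = 275 | 225 |

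**Allocation under 6.2.1.10 alone.** 500/2 = 250 side and 250 front. With at least 200 US subjects, 250 − 150 = 100 subjects change position. Odd counts at sites could shift either group by at most 30/2 = 15 to 50/2 = 25 subjects, if every site had an odd count and started on the same side. That does not explain a gap of 100.

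**Events by position.** Section 8.7 expects about 25 to 30 events in 200 patients completing wear.

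- Front, 150 subjects: 25/200 × 150 = 18.75 and 30/200 × 150 = 22.5, so about 19 to 23.
- Front, 250 subjects: 31.25 and 37.5, so about 31 to 38.
- Section 8.1 attaches the same 25 to 30 events to reduced-EF patients only, about 100 of the 200. If that rate is assumed for everyone, 150 front subjects give 37.5 to 45.

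**Price of stratifying at 350/150.** If events are proportional to subjects and spread is equal, the front standard error is √(500/150) = 1.83 times the overall one, and the side standard error is √(500/350) = 1.20 times.

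**How much could pooling raw readings matter?** Suppose front and side readings differ by a constant d within-position SDs and event rates do not differ by position. With 30% front, the pooled correlation is multiplied by 1/√(1 + 0.3 × 0.7 × d²). This is 0.97 at d = 0.5, 0.91 at d = 1 and 0.74 at d = 2. All three values of d are assumptions.

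**How much could clustering matter?** Take subject-days, a pre-event window of k days, a fraction f of subjects with one event, m days of readings and no true association. The standard error that respects clustering is then √(1 + ICC × (k(1 − f)/(1 − kf/m) − 1)) times the one that ignores it. Put f = 27.5/200 = 0.1375 (midpoint of Section 8.7) and m = 63 (70% of 90 days, if wear time means days with readings).

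| Assumed window | ICC 0.1 | ICC 0.7 |
|---|---|---|
| 1 day | 0.99 | 0.95 |
| 7 days | 1.23 | 2.14 |
| 14 days | 1.46 | 3.00 |

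The answer runs from no understatement to a threefold one. It depends on a window and an ICC that the documents do not give.

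**The case against.** The best defence of the allocation is that this is a drafting gap. The design section and the allocation section agree, and 6.2.1.10 is a one-line step giving the general pattern. The full 250/250 split would need every US site to disregard both fuller sections. That is a fair limit on the likely damage. It does not remove the contradiction, because an instruction to sites should not need another section to correct it.

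The defence of the analysis is stronger. The study is observational and its methods are descriptive. Sections 8.3.1 and 8.4 name no coefficient, model, interval or unit of analysis, so there is no specified analysis that wrongly leaves out position or clustering. The more basic gap is that the primary method is undefined. No front-side offset is documented either, and offsets of up to 1 SD would cost the pooled correlation less than 10%. All of this stands, and it is why the analysis point is only a secondary improvement.

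A reader might infer that the sponsor will pool the two positions and treat days as independent, with intervals too narrow by a known factor. The documents do not say that either will be done, and they do not commit to any interval. Nor can a factor be derived: with a 1-day window the calculation above shows no understatement at all.

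**Conclusion.** Step 6.2.1.10 is wrong as written in the sense that it cannot be followed together with 3.1.1 and 8.2. That rests on the text alone. The size is about 250/250 against 350/150, conditional on at least 200 US subjects; the gap shrinks as US enrolment falls below 200. The documents do not show which allocation sites actually used, so the contradiction should not be read as evidence that the lead-in block was lost.

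Reporting by position is worth doing because position is already allocated and, under 3.1.1 and 8.2, is tied to region and enrolment period. It is an improvement and not the repair of an error. The estimate of 19 to 23 front events rests on the Section 8.7 rate and the 350/150 split. Clustering matters only if an interval is reported on repeated readings, and its size is undetermined.

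**What to change.** 1. Reconcile 6.2.1.10 with 3.1.1 and 8.2, for example by having the step refer to the 8.2 allocation scheme. Cost: one line.
2. In 8.3.1 or 8.4, state that the primary correlation will be reported overall and by patch position. Any front-versus-side comparison should use only concurrently alternated subjects (150 and 150 if at least 200 US subjects enrol). The Visit 1 list does not mention recording the position worn, so confirm that the case report form captures it. Cost: a sentence, a little programming, and position-specific estimates that are less precise and should be labelled descriptive.
3. Add that any interval based on repeated daily readings will use a subject-clustered variance. Cost: a sentence, and possibly wider intervals. Quote no inflation factor unless the pre-event window is fixed and the within-subject correlation is known.

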8.3 Endpoint Assessment

8.3.1 Primary endpoint

The first primary endpoint will be assessed by the strength of the correlation between μ Cor device readings and heart failure related clinical events.

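### The primary correlation makes no provision for day since discharge, so a reading that merely drifts with recovery could appear to be associated with heart failure events

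*Combined protocol and SAP*

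**What the plan says.** The primary objective (2.1.1) concerns heart failure events within 90 days of discharge. Section 8.3.1 says the endpoint will be "assessed by the strength of the correlation between μ Cor device readings and heart failure related clinical events". Section 8.4 offers descriptive statistics and qualitative analysis, and section 8.5 lists no further analysis. No section gives a coefficient, a unit of analysis, a look-back window before the event, or any matching, stratification or adjustment for time since discharge.

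On timing, section 3.1.1 states: "Subjects will be fitted with μ Cor during discharge of a heart failure related hospitalization or within a clinic visit", the clinic visit being no more than 10 days after the hospitalization. Fitting is day 0 of the study, so wear day and day since discharge can differ by up to 10 days. There is no run-in.

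On event timing, section 8.1 reads "Assuming a 20% event rate within the first 30 days in patients with reduced LVEF" and expects "at least 25-30 heart failure related events among patients with reduced EF through the length of the 90 day study period", a figure described as "accounting for not all patients reaching completion". No drop-out rate is given, and no 30-day event rate for patients with LVEF above 35%.

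**The concern.** Subjects start wear while recovering from acute decompensation. Activity, posture, respiration rate and thoracic fluid may all be expected to move over the following weeks, whether or not a new event is coming. If events also cluster early, pre-event readings come mostly from early days and event-free readings mostly from later days. Time since discharge then influences both sides of the comparison.

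The study exists to find which readings relate to heart failure events. An analysis that ignores day since discharge cannot separate a reading that warns of an event from one that is simply different in the first weeks. A larger sample does not cure this; it makes a false association look more certain.

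**Working it through.** **Inputs from section 8.1.** First cohort 200; half with reduced LVEF; 20% with an event by day 30 in that half; at least 25-30 events in that half by day 90.

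**Reproducing the plan's figure.**
- Events by day 30: 200 × 0.5 × 0.20 = 20.
- Events by day 90 at constant hazard, first events, no loss: 100 × (1 − 0.8³) = 48.8. Simple tripling gives 60.
- Neither gives 25-30. The stated total needs a falling hazard, an unstated drop-out rate, or both, so it cannot be checked from the plan's inputs.

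**Early share at face value.** 20/25 = 80% and 20/30 = 67%, against 20/48.8 = 41% under constant hazard. With no loss, the hazard ratio of days 1-30 to days 31-90 is [−ln(0.80)/30] / [−ln(0.75/0.80)/60] = 6.9 for 25 events, and 3.3 for 30 events (0.70 in place of 0.75).

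**Early share allowing for loss (loss rates are assumptions).**

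| Assumed loss | Early share |
|---|---|
| 30% of all events unobserved | 20/(30/0.7) to 20/(25/0.7) = 47-56% |
| 40% of all events unobserved | 40-48% |
| 30% of events after day 30 unobserved | 58-74% |
| 50% of events after day 30 unobserved | 50-67% |

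A constant hazard fits 25-30 events only if about 17-29% of patients are retained to day 90, assuming a constant drop-out rate. Section 7.1 anticipates wear time over 70%; that is not a retention rate, but it sits poorly with such heavy loss.

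**False difference for a reading unrelated to events.** Let the reading drift by k SD, either linearly over 90 days or over the first 30 days and then flat. In both cases the mean for days 1-30 differs from the mean for days 31-90 by 0.5k. With person-days spread evenly, one third lie in days 1-30. If a share p of events is early, the difference between event days and all days is

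d = 0.5 × k × (p − 1/3), with AUC ≈ Φ(d/√2).

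| p | d, k = 1 | AUC | d, k = 2 | AUC |
|---|---|---|---|---|
| 0.80 | 0.23 | 0.57 | 0.47 | 0.63 |
| 0.67 | 0.17 | 0.55 | 0.33 | 0.59 |
| 0.50 (daily rate ratio 2) | 0.08 | 0.52 | 0.17 | 0.55 |

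The ratio of 2 corresponds, for example, to 30 observed events with half of those after day 30 lost: 10/0.5 = 20 late events, and (20/30)/(20/60) = 2.

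**Simulation check.** Readings unrelated to events; 300 runs per scenario; between- and within-patient SD 0.7 each; lag-1 autocorrelation 0.8; linear drift; 20 events per 100 patients by day 30. All of these except the event counts are assumptions. The plan names no test, so the last two columns show what a 5% test on pooled days would do.

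| Drift | Events per 100 by day 90 | Pooled AUC | False positives, 100 patients | False positives, 250 patients |
|---|---|---|---|---|
| 0.5 SD | 25 | 0.53 | 6% | 16% |
| 1 SD | 25 | 0.56 | 17% | 41% |
| 1 SD | 30 | 0.54 | 12% | 24% |
| 2 SD | 25 | 0.61 | 48% | 85% |
| 2 SD | 30 | 0.57 | 27% | 57% |

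The 250 column is the reduced-LVEF half of the full 500. Comparing patients only with others at risk on the same day gave false-positive rates of 2-8% across the scenarios, near nominal. Under constant hazard, with or without drop-out, the pooled day-level AUC was 0.50 even with 2 SD drift. A patient-level mean cut off at the event was biased even then: AUC 0.60 at 1 SD without drop-out.

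**The case against.** The strongest reply is that the plan specifies no particular correlation. Within-subject change, patient-level summaries or a matched analysis would all fit its wording. A reader might infer that the plan pools all wear days; it does not say so. The defect is an omission that permits pooling.

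Three further inferences also go beyond the documents:

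- **That most events in the whole study fall early.** The 20% rate covers only the reduced-LVEF half. Section 8.7 gives the same 25-30 events for all 200 patients completing wear, which is a different base from section 8.1, and the two should be reconciled.
- **That the plan's figures fix a daily event rate 4 to 8 times higher early.** That comes from (20/30)/(10/60) to (20/30)/(5/60). It treats a floor as a count and divides a total that is net of drop-out by full person-time.
- **That every drifting reading will correlate with events.** The effect is small for a 0.5 SD drift and absent at day level under constant hazard. The documents give no drift size.

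All of this stands and limits the size of the claim. It does not remove the gap: nothing in section 8 excludes an analysis confounded by time since discharge, and the expected event figures are hard to reconcile with a constant hazard without very heavy loss.

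**Conclusion.** The concern holds as a gap in specification. The primary association is left as an unadjusted correlation, in patients who start wear during recovery, with no provision for day since discharge. If days are pooled and the hazard falls among those still at risk, a 1 SD recovery drift in a reading unrelated to events yields a false difference of about 0.08-0.23 SD (AUC about 0.52-0.57 by formula, 0.54-0.56 in simulation at the face-value event figures). A 2 SD drift doubles the difference.

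This rests on an assumed drift and on an early share of 50-80% of events. The upper end is section 8.1 at face value, for reduced LVEF only; heavier loss could bring the share lower. The case for action is that the bias is avoidable, and that it would otherwise look more convincing as the sample grows.

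**What to change.** State in section 8.3.1 that the primary association is estimated at equal time since discharge:

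- **Model:** a Cox model on the days-since-discharge scale, with the reading as a time-varying covariate. Subjects enter at their fitting day (delayed entry, since fitting may be up to 10 days after discharge), and the window closes 90 days after discharge. Day-matched risk sets, comparing a subject before an event with subjects still event-free on the same day since discharge, are an acceptable alternative.
- **Look-back window:** a fixed interval before the event, chosen before the data are examined.
- **Patch position:** stratify by front or side, because section 8.2 assigns the first 200 US subjects to the side only and alternates the rest.
- **Unadjusted correlation:** report as descriptive only.

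Section 8.1 should also state its drop-out assumption and be reconciled with section 8.7 on which patients the 25-30 events refer to.

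The cost is section 8 wording and a little more programming. Wear start is recorded (6.2.1.13), and the discharge date is needed to apply inclusion criterion 4.1.1, but section 6.2.1 does not list it as a recorded item, so the sponsor should confirm that the eCRF holds it. The downside is that reported associations may be smaller.
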